Invasive CPET with hemodynamic monitoring using right heart catheterization: Participants with dyspnea and (1) clinically-indicated RHC or CPET based on referral by primary physician, or (2) abnormal PASP by screening echo and other criteria outlined above will be taken to the cardiac catheterization laboratory. Under sterile conditions, a pulmonary artery catheter will be placed using standard procedures and fluoroscopic guidance. In brief, topical lidocaine will be used to numb up the site of entry. A high-fidelity 7F balloon-tipped catheter is then inserted in the internal jugular vein under sterile conditions using ultrasound guidance. The catheter is then advanced into the right atrium, right ventricle (through the tricuspid valve), and pulmonary artery (through the pulmonary valve) into wedge position, guided by pressure tracings as well as fluoroscopic guidance. It will be used to measure resting right atrial, right ventricular, pulmonary artery, and pulmonary capillary wedge pressure (RA, RV, PA, PCWP). Fick cardiac output (CO), cardiac index, systemic vascular resistance, and pulmonary vascular resistance will be calculated. Pulmonary hypertension will be defined as resting mean PA pressure >20mmHg. 94,107 Resting hemodynamics will be obtained. The participant will then be transferred to the MGH CPET Laboratory (next door to the cardiac catheterization laboratory) for the exercise portion. Resting spirometry, blood pressure, 12-lead electrocardiogram, gas exchange, and heart rate will be measured. Participants will then undergo maximum incremental upright cycle ergometry at 5 to 15 W/min continuous ramp after an initial 3 minute period of unloaded exercise. 65 Hemodynamic measurements will be made (Table 2), and data analyzed in BreezeSuite (MedGraphics, St. Paul, MN). In brief, right atrial, PA, and PCWP will be measured in the upright position at end-expiration while seated at rest on the bicycle, and repeated at 1-minute intervals during exercise. Fick CO will be measured using standard technique, and peak oxygen uptake (VO2) will be defined as the highest VO2, averaged over 30s during the last minute of symptom-limited exercise. 95 We have safely performed over 1,000 tests without significant adverse events. Objective established criteria for CPET termination include ischemic electrocardiographic changes, complex arrhythmias, symptomatic fall in systolic blood pressure > 20mmHg, marked hypertension (> 240/120 mmHg), and severe desaturation < 80%.

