Visit 5 (Final measures): At the fifth study visit approximately 3 months ( $\pm$  2 weeks) after initiation of metformin or placebo, final measures will be obtained. Seated blood pressure and pulse will be obtained. Blood work will be obtained. We will collect up to 150 ml of blood for these measurements and storage of samples for future use. Participants will then undergo invasive CPET with hemodynamic monitoring and PAEC cell collection as outlined previously. In order to minimize participant burden, repeat invasive CPET testing may be conducted without invasive arterial monitoring or first-pass radionuclide ventriculography.

Study staff members are available for questions at any time throughout the study, and contact numbers are provided to the subject. At the end of each study visit, participants will be given the opportunity to ask any questions regarding the study.

Research subjects who complete the study will be compensated for their time and efforts, according to each visit completed as follows: Visit 1 \$50, Visit 2 \$150, Visit 3 \$50, Visit 4 \$50, Visit 5 \$250. If the subject withdraws from the study, they will receive payment for the visits that were completed. Subjects will be paid upon completion of each visit. We will also provide parking vouchers for study visits.

Additional Visits: If a visit involving invasive CPET (Visit 2 or Visit 5) is scheduled more than 30 days after Visit 1 or Visit 4, respectively, then research subjects may be asked to attend an additional visit

prior to CPET in order to obtain pre-requisite labs and electrocardiogram guided by cath lab safety protocols. Subjects will be compensated \$50 and a parking voucher for each such additional visit.

Research subjects may be asked to complete a COVID test (e.g. nasopharyngeal swab) prior to procedures, such as the CPET. This follows institutional guidelines to ensure the safety of hospital staff and patients. Required pre-procedure COVID testing will be paid for by the study fund. Subjects will be compensated \$20 per COVID test.

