	RV	Right ventricular pressure	2, 5
	PA	Pulmonary arterial pressure	2, 5
	PCWP	Pulmonary capillary wedge pressure	2, 5
	CO TD	Cardiac output – thermodilution	2, 5
	CO Fick	Cardiac output – Fick	2, 5
	$\overline{\text{RER}}$	Respiratory exchange ratio	2, 5
	VO2	Oxygen uptake	2, 5
	VCO2	Carbon dioxide output	2, 5
	VT	Ventilatory threshold	2, 5
	Work	Work load (watts)	2, 5
	VE	Minute ventilation	2, 5
	Vitals	Blood pressure, heart rate, oxygen saturation during	2, 5
	RVEF	exercise	2
	LVEF	RV function rest and exercise	2
	LVEF		

\* optional

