Protection against risk: We are recruiting participants from two sources: (1) patients who are referred for clinically indicated RHC and CPET by other physicians. In such cases, RHC and CPET are being performed for clinical reasons regardless of our research study; (2) study volunteers that undergo rigorous screening procedures prior to RHC and CPET in order to justify testing for pure research purposes. To assure a reasonable balance in risk versus benefit ratio among the latter group, we will perform studies on individuals who have dyspnea and abnormal estimated PASP (defined as >40mmHg) based on noninvasive imaging, where testing has been deemed reasonable as outlined by expert clinical consensus. 94 Right heart catheterization procedures will be performed at the MGH cardiac catheterization laboratory by licensed and board-certified interventional cardiologists. All safety protocols in place will be followed. Prior to the procedure, we will verify that the participant is at low bleeding risk by checking a complete blood count and coagulation profile. Only individuals with INR <1.5 and platelet counts > 75,000 will be eligible for right heart catheterization (see inclusion/exclusion criteria). In addition, we will perform pregnancy testing in women of child-bearing age and exclude anybody with a positive test. After verifying informed consent, a procedure time-out will be performed. Usual sterile technique will be used, and ultrasound guidance and fluoroscopy will be used to place the pulmonary artery catheter to minimize risks of the procedure. The participant will be monitored continuously with blood pressure, heart rate, and telemetry. In order to minimize the risk to the participant during CPET testing, physician supervision will be mandated for all exercise assessments. Participants with contraindications to exercise testing will be excluded (Table 1). The laboratory will have resuscitation equipment and Advanced Cardiac Life Support-trained physicians and exercise technicians. Ratings of perceived exertion and dyspnea will be monitored during testing, as will heart rate, blood pressure, and continuous electrocardiographic tracings and test will be terminated by the test operator per standard exercise testing guidelines (i.e. a > 10mmHg fall in blood pressure, ventricular tachycardia).

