#### **Definitions of AEs and SAEs**

**Adverse events** will be defined as "any untoward or unfavorable medical occurrence in a human subject, including any abnormal sign, symptom, or disease, temporally associated with the subject's participation in the research, whether or not considered related to the subject's participation in the research". Specifically for this study, this will include the following:

Procedure	Expected Potential Adverse Event
Phlebotomy	Discomfort, bruising, bleeding, lightheadedness, fainting
6-minute walk test	Dyspnea, chest pain, leg cramps, diaphoresis.
Oral glucose tolerance test	Hyperglycemia, nausea, stomach discomfort, diarrhea, and constipation.
Echocardiography	Discomfort
Invasive cardiopulmonary exercise testing	Uncommon: Allergic reaction to local anesthetic, pain, bleeding, infection, hypo- or hypertension during exercise, fainting during exercise, arrhythmia, chest pain
	Rare: injury to the nerve around catheter insertion site, pneumothorax, air embolism, blood clot, vascular or myocardial perforation, pericardial effusion, myocardial ischemia/infarction, sustained arrhythmia or hemodynamic instability.
Metformin therapy	Common: Diarrhea, nausea, vomiting, flatulence, weakness Less common: cardiovascular: chest discomfort, flushing, palpitations, headaches, dizziness, lightheadedness; gastrointestional: indigestion, abdominal discomfort or distention, abnormal stools, constipation, dyspepsia/ heartburn, taste disorder; respiratory: dyspnea, upper respiratory tract infection; general: chills, rash, myalgia, hypoglycemia, decreased vitamin B 12 levels, increased diaphoresis, flu-like syndrome, nail disorder Uncommon: lactic acidosis, leukocytoclastic vasculitis, megaloblastic anemia, pneumonitis, anaphylaxis.

**Serious adverse events** will be defined as "any adverse event that results in death, is life-threatening, results in hospitalization, persistent disability, congenital anomaly, or based upon appropriate medical judgment, may jeopardize the subject's health and may require medical or surgical intervention to prevent one of the other outcomes listed in this definition". Specifically for this study, this will include the following:

Procedure	Expected Potential Serious Adverse Event
Invasive cardiopulmonary	Rare: injury to the nerve around catheter insertion site,
exercise testing	pneumothorax, air embolism, blood clot, vascular or myocardial

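### The protocol states two different blood-pressure thresholds for stopping the same invasive exercise test, and neither section refers to the other

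*Protocol*

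**What the plan says.** Section 5 of the protocol, in the paragraph on invasive CPET with right heart catheterization, lists when the test is stopped: "Objective established criteria for CPET termination include ischemic electrocardiographic changes, complex arrhythmias, symptomatic fall in systolic blood pressure > 20mmHg". The same sentence goes on to limits for very high pressure (above 240/120 mmHg) and for oxygen saturation below 80%.

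Section 7 covers the same procedure. Its protection-against-risk paragraph says the "test will be terminated by the test operator per standard exercise testing guidelines (i.e. a > 10mmHg fall in blood pressure, ventricular tachycardia"). The same paragraph requires that "physician supervision will be mandated for all exercise assessments".

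The test is done at Visit 2 and again at Visit 5: "Participants will then undergo invasive CPET with hemodynamic monitoring and PAEC cell collection as outlined previously". Table 2 schedules exercise vital signs at both visits ("Blood pressure, heart rate, oxygen saturation during" exercise). In Section 9, the table of expected adverse events for invasive CPET includes: "Uncommon: Allergic reaction to local anesthetic, pain, bleeding, infection, hypo- or hypertension during exercise, fainting during exercise, arrhythmia, chest pain".

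**The concern.** A stop threshold is a decision rule that an operator applies in real time during maximal exercise with a catheter in the pulmonary artery. Here the rule is stated twice, with different figures, and each statement presents itself as the standard one: Section 5 as established criteria, Section 7 as what exercise-testing guidelines require.

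The stricter figure is in the section that tells the IRB how participants are protected. The looser figure is in the procedures section, where staff would naturally look for the stop rule. If the test is run from Section 5 alone, participants may get less protection than Section 7 states. Some are volunteers tested purely for research, and Section 8 expects no direct benefit for participants.

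**Working it through.** The protocol gives no figure to reproduce here, so the check sets the two criteria side by side.

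**Step 1. How they differ.**

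| Element | Section 5 | Section 7 |
|---|---|---|
| Size of fall | more than 20 mmHg | more than 10 mmHg |
| Symptoms | required | not mentioned |
| Pressure named | systolic | not specified |
| Reference reading | not given | not given |

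**Step 2. What each requires for a given fall.** This assumes that both measure the fall from the same reference reading and that Section 7 covers a systolic fall.

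| Systolic fall | Symptoms | Section 5 blood-pressure criterion | Section 7 |
|---|---|---|---|
| 10 mmHg or less | either | not met | not met |
| more than 10 to 20 mmHg (e.g. 15) | no | not met | stop |
| more than 10 to 20 mmHg (e.g. 15) | yes | not met | stop |
| more than 20 mmHg (e.g. 30) | no | not met | stop |
| more than 20 mmHg (e.g. 30) | yes | stop | stop |

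**Step 3. Can both be obeyed?** Yes. A fall above 20 mmHg is also above 10 mmHg, so every fall that meets the Section 5 criterion also meets the Section 7 one. Stopping at more than 10 mmHg complies with both, but it leaves the Section 5 criterion with nothing to do.

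**Step 4. Where they part.** Two kinds of fall are covered only by Section 7: a symptomatic fall of more than 10 and up to 20 mmHg, and an asymptomatic fall of more than 10 mmHg with no upper limit. A test in either group could still be stopped on another Section 5 ground, such as an arrhythmia, but not on blood pressure.

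**Step 5. Does any text settle it?** Neither section cites the other. The adverse-event tables in Section 9 set no threshold. The stopping rules there concern ending the whole protocol, not a single test. The SAP does not address the matter.

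**Step 6. How often?** This cannot be calculated. Section 9 classes exercise hypotension and fainting as uncommon and gives no rate.

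**The case against.** The best defence is that there is no operational conflict. Section 7 is mandatory in its wording. The Section 5 list is open, because it says what the criteria include, not what they are limited to. A careful operator who reads the whole protocol stops at more than 10 mmHg, under a supervising physician. This largely stands, and it is why the point is minor. It does not explain why Section 5 carries a threshold that would then never be used. Nor does supervision tell the physician which fall ends the test.

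Several stronger readings are tempting, and the documents do not support them:

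- **That Section 5 tells the operator to continue through a fall below 20 mmHg.** It gives no such instruction; it only lacks a blood-pressure criterion there.
- **That Section 7 drops ischemia, hypertension and desaturation as reasons to stop, because its list is shorter.** Section 7 points to outside guidelines and gives a parenthesis. Section 5 names all three, and nothing withdraws them.
- **That Section 7 covers every fall above 10 mmHg without exception.** It sets no symptom condition, but it does not say so in those terms.
- **That continuous monitoring ensures a fall during exercise is seen.** The sentence "The participant will be monitored continuously with blood pressure, heart rate, and telemetry" sits with the catheter-placement text, before the paragraph turns to exercise. Table 2 is the clearer support for blood pressure being recorded during exercise.

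Scope also narrows the point. Section 7 says clinically referred participants have these tests for clinical reasons regardless of the study. Section 5 lets participants with a previous clinical CPET skip the Visit 2 test. For the latter, the ambiguity mainly concerns Visit 5.

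**Conclusion.** The inconsistency is real and is in current text for the same procedure. The thresholds differ by 10 mmHg (20 − 10), in the symptom condition and in the pressure named. Relying on Section 5 alone leaves two kinds of fall without a blood-pressure stop criterion, which is less protection than Section 7 states. The comparison rests on a common reference reading, which neither section gives, and on Section 7 applying to systolic falls.

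This is a minor safety-text correction. A reader might infer that the two rules bias the slope of pulmonary artery pressure against cardiac output, or reduce power. The documents give nothing to support that, and no effect on endpoint, alpha or power is claimed. The number of participants affected is unknown.

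**What to change.** Put one identical blood-pressure criterion in Sections 5 and 7. It should name systolic pressure, the reference reading and whether symptoms are required. Use the stricter figure unless the investigators and the IRB choose otherwise. For example: end the test if systolic pressure falls by more than 10 mmHg from the stated reference reading, with or without symptoms. The investigators choose the reference, such as seated rest on the cycle or the preceding reading.

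Keep the full stop list in Section 5, have Section 7 refer to it, and say that it applies to research CPETs at Visits 2 and 5.

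The cost is a wording amendment with IRB review, with no added participants or procedures. The downside is that some tests may stop earlier. Pressures are "repeated at 1-minute intervals during exercise", so each minute lost removes one exercise reading from that participant's slope.

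The same amendment could add one sentence to Section 5 saying that the 450 cc study cap on blood in Section 7 overrides the per-visit maxima, which reach 100 + 150 + 100 + 100 + 150 = 600 ml when all five visits are separate.

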#### Drugs to be used

A total of 75 subjects will be randomized to 3-months of metformin or matching placebo. Participants will be given 500mg capsules of metformin or matching placebo and instructed to take 500mg twice daily for 1 week, followed by 1g twice daily for a total of 3 months. Metformin is widely used in the treatment of insulin resistance found in diabetes mellitus, and meta-analyses have shown metformin to be safe for use in heart failure,  and in the absence of hyperglycemia.  We will exclude individuals with contraindications to metformin use (**Table 1**), and participants will be monitored for clinical symptoms of lactic acidosis and hypoglycemia. Medication compliance will be assessed with pill counts. The proposed use of metformin is IND-exempt.

# Repository activities

As part of the informed consent, participants will be asked whether blood, not used in this analysis, may be stored for future analysis. If the participant does not consent to this, samples will be used only for the present study and excess samples discarded. All samples will be processed immediately and stored at -80°C for future analysis. Samples will be labeled with study identification numbers only – no other identifiable information will be attached to the samples. Samples will be stored in a locked freezer in a private space, and only co-investigators will have access. Such samples could be used to measure the effects of metformin on circulating markers of endothelial function, or other blood markers related to the causes of cardiovascular disease, depending on the findings of the study. No immortalized cell lines will be created from the harvested cells.

Table 2. Data to be collected (see attached CRFs)

Type	Variable	Description	Study Visit
Demogr	Age		1
aphic	Sex		1
•	Race		1
	Ethnicity		1
Exam	Height		1, 4
	Weight		1, 3*, 4
	BP	Blood pressure	1, 2, 3*, 4, 5
	HR	Heart rate	1, 2, 3*, 4, 5
	Waist	Waist circumference	1, 4
History		Medical history as outlined in CRF	1
ECG		12-lead electrocardiogram	1, 4
Lab	CMP	Comprehensive metabolic panel	1, 2, 3, 4, 5
	CBC	Complete blood count without differential	1, 4
	Lipids	Fasting lipid panel	1
	CRP	C-reactive protein	1, 4

	NT-proBNP	N-terminal pro B-type natriuretic peptide	1, 4
	INR	International normalized ratio (blood coagulation)	1, 4
	Adiponectin	Total adiponectin concentrations	1, 4
	Blood HCG	Blood pregnancy test (women only)	1, 2, 3, 4, 5
	Glucose		1, 4
	Insulin		1, 4
	Blood gas	Oximetry during CPET	2, 5
	Alc	Hemoglobin A1c	1, 5
	Lactic acid		3
Echo	LVEF	Simpson's modified biplane LV ejection fraction	1
	LVDD	LV end-diastolic dimension	1
	LVSD	LV end-systolic dimension	1
	LAD	Left atrial end-systolic diameter	1
	LVWT	LV wall thickness = posterior + septal wall thickness	1
	RWT	Relative wall thickness = LVWT/LVDD	1
	FS	Fractional shortening = $[(LVDD-LVSD)/LVDD] x$	1
	LVM	100	1
	Е	LV mass = $0.8 [1.04 ((LVDD+LVWT)^3 -$	1
	A	$(LVDD)^3$ ]+0.6.(1)	1
	DT	Early mitral inflow velocity on Doppler	1
	E'	Late mitral inflow velocity on Doppler	1
	PAAT	Deceleration time of early mitral inflow on Doppler	1
	TR jet	Early mitral annular velocity on tissue Doppler	1
	3	Pulmonary artery acceleration time	
		Tricuspid regurgitation jet velocity	
CPET	RA	Right atrial pressure	2, 5
	RV	Right ventricular pressure	2, 5
	PA	Pulmonary arterial pressure	2, 5
	PCWP	Pulmonary capillary wedge pressure	2, 5
	CO TD	Cardiac output – thermodilution	2, 5
	CO Fick	Cardiac output – Fick	2, 5
	$\overline{\text{RER}}$	Respiratory exchange ratio	2, 5
	VO2	Oxygen uptake	2, 5
	VCO2	Carbon dioxide output	2, 5
	VT	Ventilatory threshold	2, 5
	Work	Work load (watts)	2, 5
	VE	Minute ventilation	2, 5
	Vitals	Blood pressure, heart rate, oxygen saturation during	2, 5
	RVEF	exercise	2
	LVEF	RV function rest and exercise	2
	LVEF		

\* optional

#### **6. BIOSTATISTICAL ANALYSIS**

**Aim 1:** To investigate the association of metabolic disease and PAEC phenotypes with pulmonary hemodynamics in human subjects.

**Hypotheses:** Peripheral insulin resistance is associated with abnormal resting pulmonary hemodynamics. PAEC phenotype correlates with pulmonary vascular dysfunction in obese individuals.

Analysis plan for Aim 1: We will examine the association of insulin resistance (estimated by HOMA-IR^100) and pulmonary vascular hemodynamics (mean PAP and PVR by RHC) using the Pearson or Spearman correlation coefficient. Multivariable linear regression models will adjust first for age, sex, body mass index as potential confounders, and then for hypertension and smoking status. If scatter plots suggest a non-linear relationship, we will consider regression models assuming a flexible mean function such as polynomial, exponential or spline functions. We will evaluate the association of PAEC insulin signaling (insulin-stimulated eNOS phosphorylation) and pulmonary hemodynamics using linear regression. Specifically, we will examine the association of % change in the ratio of p-eNOS to total eNOS in response to insulin with mean PAP and PVR. A two-sided P-value <0.05 will be considered statistically significant for primary analyses.

Statistical power for Aim 1: In previous studies, the range of HOMA-IR among non-diabetic obese individuals was broad, with a median and inter-quartile range of 2.7 mg\*IU/dL\*mL (1.9-4.8), allowing adequate power to study associations with pulmonary vascular hemodynamics. In our preliminary CPET study, we observed a correlation coefficient of R=0.34, P<0.0001 between PASP and waist circumference (a clinical surrogate of insulin resistance). Assuming a sample size of 100 and two-sided alpha of 0.05, we have at least 80% power to detect a correlation of R≥0.28 between HOMA-IR and mean PAP (and PVR) by RHC. Further, the difference in PASP among obese individuals with and without MetS was 10mmHg in preliminary analyses. We would have 80% power to detect a ≥6mmHg difference in a two-group comparison of participants above and below the median HOMA-IR, assuming a two-sided alpha of 0.05 and a sample size of 100. With the same alpha and sample size, we would have at least 80% power to detect a correlation of R≥0.28 between PAEC insulin response and mean PAP (and PVR) by RHC.

Aim 2: To study the dynamic pulmonary vascular response to exercise in metabolic disease.

**Hypotheses:** Metabolic dysfunction is associated with abnormal pulmonary vascular hemodynamic response. PAEC phenotype correlates with exercise PAP in obese individuals

Analysis plan for Aim 2: We will relate HOMA-IR to  $\Delta$ mPAP/ $\Delta$ CO with exercise. We will test for normality of the distribution of HOMA-IR using QQ plots and the Shapiro-Wilk test. If skewed in distribution, HOMA-IR will be log-transformed. We will use random effects in linear regression models to allow repeated measures and account for multiple time points of mPAP and CO for a given individual during exercise, with HOMA-IR (or PAEC p-eNOS response) as the independent and  $\Delta$ mPAP/ $\Delta$ CO slope as the dependent variable. We will relate PAEC insulin signaling to PAP response to exercise. We will use a random effects model with % change in the ratio of p-eNOS to total eNOS in response to insulin as the independent, and  $\Delta$ mPAP/ $\Delta$ CO as the dependent variable. All analyses will be adjusted for age, sex, and body-mass index, and additionally adjusted for resting blood pressure and smoking status.

Statistical power for Aim 2: In preliminary analyses, the  $\Delta$ mPAP/ $\Delta$ CO slope in diabetics versus non-diabetics was 3.4±1.3 mmHg/L compared with 2.6±1.3 mmHg/L. Assuming a sample size of 100

participants and a two-sided alpha of 0.05, we would have 86% power to detect a similar difference in  $\Delta mPAP/\Delta CO$  slope among individuals above and below the median HOMA-IR. We would have at least 80% power to detect a correlation of R=0.28 or greater between PAEC insulin response (% increase in p-eNOS) and the  $\Delta mPAP/\Delta CO$  slope.

**Aim 3:** To examine the effect of metformin on pulmonary vascular function and PAEC phenotype in obese individuals.

**Hypotheses:** Metformin will improve pulmonary vascular hemodynamics compared with placebo. Metformin will improve insulin signaling in human PAECs compared with placebo.

Statistical analyses for Aim 3: We will compare the change in  $\Delta mPAP/\Delta CO$  slope in the metformin vs placebo groups. The "delta" in slope will be defined as the 3-month minus the baseline value. We will apply a two-sample t-test to compare the delta in the two groups in an unadjusted intention-to-treat analysis. An adjusted analysis will be performed using a multivariable random effects linear regression model adjusted for baseline  $\Delta mPAP/\Delta CO$ , such that [delta  $\Delta mPAP/\Delta CO$ ] = intercept +  $\beta_1$ \*treatment group +  $\beta_2$ \* $\Delta mPAP/\Delta CO_{baseline}$ , with treatment group and  $\Delta mPAP/\Delta CO_{baseline}$  as fixed effects and treatment group modeled as a random effect. Given that the randomization will be stratified by type of pulmonary vascular dysfunction (resting versus exercise-induced), we will use a 'strata' statement to indicate PH type in the model. We anticipate that metformin will improve PAEC insulin resistance (% change in the ratio of p-eNOS to total eNOS) and also pulmonary hemodynamics. In secondary analyses, we will examine the correlation between PAEC and venous endothelial cell insulin resistance among treatment groups.

Statistical power for Aim 3: We will power the study for the between-group comparison (metformin vs placebo) of the delta in  $\Delta$ mPAP/ $\Delta$ CO (3 month – baseline). In 15 prior patients with repeat testing within 12 weeks, the reproducibility of  $\Delta$ mPAP/ $\Delta$ CO was robust, with an intra-individual CV of 0.92, and a standard deviation (SD) of the delta (12-week minus baseline) of 0.46. We will assume a similar SD in this study. In our experience with intervention studies, attrition from non-compliance is ~15%. With a target enrollment of 75 participants and 15% loss to follow-up, we would have 64 participants completing the study. In preliminary studies, the difference in  $\Delta$ mPAP/ $\Delta$ CO slope among diabetics and non-diabetics was 0.7mmHg/L. We estimate >80% power to detect up to 50% of the difference in  $\Delta$ mPAP/ $\Delta$ CO between diabetics vs nondiabetics (0.35mmHg/L) among the treatment groups using a two-sided t-test with 5% type I error.

